8.6. ECG

A summary of ECG parameters (heart rate, PR, QRS, QT, and QTc intervals) and change from baseline will be presented for each planned visit. When triplicate assessments were taken at a visit, the median value will be used for summary purposes.

The ECGs will be assessed by the investigator and deemed, from best to worst finding, “Normal”, “Abnormal, not clinically significant” or “Abnormal, clinically significant”. Shifts in this overall interpretation between baseline and the worst overall assessment will be tabulated.

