6.7 Electrocardiograms

Screening and predose ECGs (if required) are to be performed in triplicate (5-10 min between readings). ECGs are to be performed after the patient has been supine for at least 10 minutes. All ECGs should be performed with the patient in the same physical position. Postdose ECGs (if required) are to be performed in triplicate (5-10 min between readings) only if patient has a QTc that is a) >500 msec; b) increased by 60 msec over pre-dose; or c) decreased by 50 msec below pre-dose recording.

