¹ A pre-treatment biopsy or archival sample is required for p53 testing. For patients with a study biopsy performed immediately prior to enrollment, optional needle biopsy to be performed within 24 hours of Cycle 1 Day 15 infusion OR Cycle 2 Day 15 infusion. Decision to be made at the discretion of the Investigator. In EXP, optional biopsies include pre-treatment, during treatment, and one or more at times of suspected and/or confirmed progression.

² Can be omitted if screening laboratory assessments are performed within 7 days of the first dose of ALRN-6924. Screening/within 7 day assessments are to be used for eligibility assessment.

³ HPV status must be determined for tumors that are associated with HPV infection, including (but not limited to) cervical cancers, oropharyngeal cancer, head and neck squamous cell cancers or anal cancer, unless HPV status of the tumor is already known and documented.

⁴ Blood pressure, pulse, respiration rate, body temperature.

Cycle 1, Days 1, 8, 15: On the days of drug administration vital signs will be recorded pre-dose (within 30 minutes prior to SOI) and at the following timepoints:

During infusion:

DR-A (one hour infusion): 15 min (± 3 min) and 30 min (± 3 min)

DR-A-2 (two hour infusion): 30 min (± 3 min) and 60 min (± 3 min)

Post-infusion: At EOI (±5 min), 1 hr (±5 min) and 2 hr (±10 min), 4 hrs (±10 min) following EOI. On Cycle 1 Day 1 additional timepoints include 6 hrs (±10 min) and 8 hrs (±10 min) following EOI. Additional vital signs will be collected at the discretion of the investigator.

⁵ Full physical examination to be performed at Screening, Day 1 Predose, and End of Treatment; all other physical examinations may be symptom directed. Height and weight to be collected on Day 1.

⁶ ECGs to be performed after the patient has been supine for at least 10 minutes. Readings should be performed with the patient in the same physical position. Screening and pre-dose ECG recording should be taken in triplicate with 5-10 minutes between readings. Thereafter, subsequent readings on that same day will be performed in triplicate only if patient has a QTc that is a) >500 msec; b) increased by 60 msec over pre-dose; or c) decreased by 50 msec below pre-dose value. Timepoints on Cycle 1, Day 1: Pre-dose (within 30 minutes prior to infusion), end of infusion (EOI +5 min) and at 1 (± 5 min) and 2 hr (±10 min) after EOI.

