³ Full physical examination to be performed at End of Treatment visit; all other physical examinations may be symptom directed. For patients on $>$ 1 year, this procedure is no longer a mandatory study procedure. Weight to be collected at Day 1 (+/- 3 days) of each cycle.

⁴ ECGs to be performed after the patient has been supine for at least 10 minutes. Readings should be performed with the patient in the same physical position. Pre-dose ECG recording should be taken in triplicate with 5-10 minutes between readings. Thereafter, subsequent readings on that same day will be performed in triplicate only if patient has a QTc that is a) $>$ 500 msec; b) increased by 60 msec over pre-dose; or c) decreased by 50 msec below pre-dose value. Timepoints on Day 1 of new cycle: At pre-dose (within 30 minutes prior to infusion) and EOI (+5 min). For patients on $>$ 1 year, this procedure is no longer a mandatory study procedure.

⁵ For patients on $>$ 1 year, the required labs are: full labs to be collected on Day 1, and hematology only at Day 15

⁶ Within 1 hour before SOI

⁷ PK (Cycle 2 only): Day 15-collect at EOI (+5 min) and at 1 hour (\pm 5 min) and 4 hours (\pm 10 min) after the end of infusion. Patients who are already enrolled in the expansion and consent to this PD/PK testing will have blood drawn at their next available cycle (i.e. if the next available cycle is Cycle 4, they will follow the PK/PD Cycle 1 testing at Cycle 4, and will follow the indicated Cycle 2 testing at Cycle 5).

PK (Cycle 2 only): DEP only - Day 16 - Blood should be collected 24 hours (\pm 4 h) after the initiation of Day 15 infusion.

⁸ Day 16 visit should only be completed for Cycle 2; this visit to be completed in DEP and only in EXP if the optional biopsy is performed

⁹ For patients on $>$ 1 year, this is no longer a mandatory study procedure

¹⁰ Cycle 2 biopsy not performed if collected in specified timepoint in Cycle 1. For patients with a study biopsy performed immediately prior to enrollment, optional needle biopsy to be performed within 24 hours of Cycle 1 Day 15 infusion OR Cycle 2 Day 15 infusion; decision to be made at the discretion of the Investigator. In EXP, optional biopsies include pre-treatment, during treatment, and one or more at times of suspected and/or confirmed progression.

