3.2.1.1. Baseline and Change from Baseline

Baseline value is defined as the last value obtained before the first dose of study treatment administration. This value could be the pre-dose assessment on C1D1 or an assessment obtained during screening. Change from baseline = (post-baseline value - baseline value).

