8.5. VITAL SIGNS

Vital signs (respiratory rate, temperature, blood pressure, and heart rate) are assessed periodically during and after each infusion. The data analysis of these data will consist of two phases:

- For cycles 1 and 2, each subject's values at each time point and the changes from pre-infusion to each follow-up assessment within the cycle will be summarized.

- For cycle 3 and beyond, the average of each subject's values for each time point across cycles and the changes from pre-infusion average to each follow-up time point average will be summarized.

Additionally, the changes from baseline to max and min post-baseline values will be summarized.

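### SAP 8.6 summarises QTc by visit with a triplicate median and has no rule for time points within the visit; read literally, it drops or dilutes any end-of-infusion QTc change

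*SAP*

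**What the plan says.** **SAP.** Section 8.6 covers heart rate and the PR, QRS, QT and QTc intervals. Its rule is: "change from baseline will be presented for each planned visit. When triplicate assessments were taken at a visit, the median value will be used". It names no time point within a visit. The only other ECG table is a shift from baseline to the worst of the investigator's three-level overall interpretation.

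Section 3.2.1.1 says: "Baseline value is defined as the last value obtained before the first dose of study treatment administration". It allows this to be the Cycle 1 Day 1 pre-dose assessment or a screening one. Section 3.4, which covers ECG data, mentions summaries by time point but assigns scheduled assessments by the sites' visit designations. Section 8.5, on vital signs, is explicit about time points in the first two cycles: "each subject's values at each time point and the changes from pre-infusion to each follow-up assessment within the cycle will be summarized".

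**Protocol.** Under section 6.7, screening and pre-dose ECGs are always triplicate, 5-10 minutes apart. Post-dose ECGs are done "in triplicate (5-10 min between readings) only if patient has a QTc that is a) >500 msec". The other two triggers are a rise of 60 msec over pre-dose and a fall of 50 msec below it.

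Appendix C, footnote 6 (regimens A and A-2, Cycle 1) gives: "Timepoints on Cycle 1, Day 1: Pre-dose (within 30 minutes prior to infusion), end of infusion (EOI +5 min". It adds readings 1 and 2 hours after the end of infusion. Appendix D, footnote 4 (Cycle 2 onward) gives: "Timepoints on Day 1 of new cycle: At pre-dose (within 30 minutes prior to infusion) and EOI (+5 min". Appendices E and F set the same time points for regimen B. Apart from screening and End of Treatment, ECGs are scheduled only on Day 1 of each cycle.

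**The concern.** The SAP's unit of summary is the visit, while the protocol's unit of measurement is the time point within the visit. At an ordinary Day 1 visit, the only triplicate is the one taken before the drug is given. A rule that takes the median when triplicates exist at the visit therefore points to the pre-dose value. The SAP gives no rule for the single post-dose readings. If a trigger is met, the visit holds two triplicates, and the SAP does not say which median counts.

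Safety is a primary objective of Phase 1. The post-dose ECGs are placed at and shortly after the end of an intravenous infusion, where an acute effect would be looked for. A by-visit table could show almost no QTc change by dose cohort even if there were a clear one at end of infusion.

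**Working it through.** The plan states no QTc figure, SD or effect size, so there is none to reproduce. The check asks what each reading of 8.6 would report for a given true effect.

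**Readings per visit, no trigger met** (Protocol 6.7 and Appendices C to F)

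- Cycle 1 Day 1: 3 pre-dose, then 1 each at end of infusion (EOI), 1 h and 2 h, so 3 + 3.
- Later Day 1: 3 pre-dose and 1 at EOI, so 3 + 1.
- A later pre-dose triplicate comes nominally 29 − 15 = 14 days (regimen A) or 22 − 11 = 11 days (regimen B) after the previous infusion. I take the residual effect as zero.

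**Assumptions.** Readings are independent and normal with SD 5, 8 or 10 msec. The true EOI effect is +20 msec. Baseline is the median of a pre-dose triplicate, with expected value 0. Medians come from simulation of 200,000 subjects per setting; means are exact.

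**Later Day 1 (3 + 1), true EOI change 20 msec**

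| Reading of 8.6 | Expected change shown |
|---|---|
| Median of the triplicate only | 0 msec |
| Median of all four readings | 2.1 (SD 5), 3.2 (SD 8), 3.7 (SD 10) msec |
| Mean of all four | (0 + 0 + 0 + 20)/4 = 5 msec |
| Average of the pre-dose median and EOI | (0 + 20)/2 = 10 msec |
| Each time point separately | 20 msec |

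**Why the median of four barely moves.** Once EOI is clearly the highest value, the median of four is the average of the middle and highest pre-dose readings. For three normal readings the expected maximum is 3/(2√π) = 0.846 SD and the expected middle value is 0. The ceiling is therefore 0.846/2 = 0.423 SD: 2.1 msec at SD 5 and 4.2 msec at SD 10. The simulation reaches these same values at a 60 msec effect. With 3 + 1 readings, the pooled median cannot show more, however large the EOI effect.

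**Cycle 1 Day 1 (3 + 3), true EOI change 20 msec**

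- Triplicate only: 0 msec by construction, because that triplicate is also the baseline.
- Median of all six, effect sustained to 2 h: 10.0 msec.
- Median of all six, effect falling to 50% at 1 h and 25% at 2 h: 4.3 to 5.2 msec.

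**Triggered later Day 1.** A 60 msec rise would normally make EOI a triplicate too (3 + 3). The pooled median then shows 30.0 msec, half the effect.

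**Worst-case summaries planned elsewhere in the SAP**

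- Laboratory data (8.4): shifts to maximum and minimum, and Grade 3 and 4 counts.
- Vital signs (8.5): changes from baseline to maximum and minimum.
- ECG intervals (8.6): neither a maximum nor a count above any threshold.

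**The case against.** The strongest reply is that 8.6 never says one value per visit. The natural purpose of the median rule is to reduce three replicates taken minutes apart to one value. SAP 3.4 says that all collected ECG data are factored into the analyses and refers to time-point summaries. A programmer might well tabulate each time point, and table shells often settle this. It stands that the defect is an unspecified rule, not an instruction to collapse the visit. But 3.4 ties tabulation to visit designations, and 8.5 shows that the authors named time points when they meant them. The text permits tables that differ as widely as 0 and 20 msec.

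Other replies also stand in part:

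- A reader might infer that the problem affects every dosing visit. It does not: on-treatment ECGs are scheduled only on Day 1 of each cycle, not on Days 8 and 15 or Days 4, 8 and 11.
- A reader might infer that the triplicate is always pre-dose. It is not: patients who meet a trigger also have post-dose triplicates.
- A reader might infer that post-dose QTc vanishes from the report. It does not. Full listings (SAP 3.1), the worst-interpretation shift, the adverse event tables and safety committee review before escalation remain. None of these, however, summarises QTc numerically by dose cohort.
- A reader might see two conflicting ECG baselines in 3.2.1.1 and 8.6. That case is weak: read together, they can mean the median of the last pre-dose triplicate. One sentence would settle it.
- The protocol's QTc values are triggers for repeat readings, not endpoints, and the analysis is descriptive. Counting them is an addition, justified because ECG intervals otherwise have no worst-case summary.
- The nonclinical hERG and monkey cardiac studies showed no significant adverse findings (Protocol 1.4.2). That does not replace a summary of the human post-dose readings.

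**Conclusion.** The point holds as a gap in specification with a material consequence if 8.6 is applied literally. At later Day 1 visits an assumed +20 msec EOI effect would show as 0 msec, about 2-4 msec or 5 msec, depending on how the four readings are reduced. On Cycle 1 Day 1 a pooled median would keep about 4-10 msec, depending on how long the effect lasts. The sizes rest on the assumed effect, SD and absence of residual pre-dose effect; the direction does not depend on the particular effect size or SD.

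The documents do not support the stronger claim that the SAP plans to discard post-infusion ECGs, nor do they show that the drug prolongs QTc. Separately, and on any reading of 8.6, no numeric worst-case QTc summary is planned. The point concerns Phase 1 only, since this SAP leaves Phase 2a to a separate plan.

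**What to change.** In SAP 8.6:

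1. Summarise ECG parameters and change from baseline by planned visit and by each protocol-scheduled time point within that visit. This wording fits Cycle 1 Day 1 (four time points), later Day 1 visits (two), screening and End of Treatment without listing time points that some visits lack.
2. Take the median only within a triplicate at the same time point.
3. State that ECG baseline is the median of the last triplicate before first dose: Cycle 1 Day 1 pre-dose, otherwise screening.
4. Add one table by dose cohort of the maximum post-baseline QTc and the maximum change. Include counts of patients with any post-dose QTc above 500 msec or an increase of at least 60 msec over pre-dose. Include unscheduled readings, as SAP 3.4 already does for extreme values.

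All the readings are already scheduled, so no new data are needed. The cost is a wording change, longer ECG tables and one extra table.

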8.7. ECOG PERFORMANCE STATUS

The ECOG performance status scores range from 0 to 5 as follows:

Grade	Description
0	Fully active, able to carry on all pre-disease performance without restriction
1	Restricted in physically strenuous activity but ambulatory and able to carry out work of a light or sedentary nature (e.g., light house work, office work)
2	Ambulatory and capable of all self-care but unable to carry out any work activities; up and about more than 50% of waking hours
3	Capable of only limited self-care; confined to bed or chair more than 50% of waking hours
4	Completely disabled; cannot carry on any self-care; totally confined to bed or chair
5	Dead

Source: Oken et al, 1982.

Shifts in ECOG performance status between baseline and the worst overall assessment will be summarized.

8.8. PHYSICAL EXAMINATION

Adverse physical examination findings with onset after the first dose of ALRN-6924 will be considered adverse events and tabulated accordingly.

9. CLINICAL ACTIVITY ANALYSES

ORR and DCR will be summarized by frequency counts, percentages, and the two-sided 95% CIs. The Wilson score method will be used to construct the confidence intervals.

The distribution of TTR and PFS will be summarized using Kaplan-Meier methodology grouped. The 25th, 50th (median), and 75th percentiles will be provided, along with their two-sided 95% CIs.

The distribution of DOR (among responders) and DCB (among subjects experiencing clinical benefit) will be summarized using Kaplan-Meier methodology grouped. The 25th, 50th (median), and 75th percentiles will be provided, along with their two-sided 95% CIs.

The best overall response (BOR) will be summarized by frequency counts and percentages of subjects achieving each possible category (complete response, partial response, stable disease, progressive disease).

10. INTERIM ANALYSES

No interim analysis is planned for this study.

11. CHANGE FROM ANALYSES PLANNED IN PROTOCOL

This statistical analysis plan is based on protocol Amendment 6, which was finalized on 20 October 2017. In addition to the endpoints outlined in the protocol, duration of clinical benefit has been included as an additional endpoint in this SAP.

